11.8 Surgical Outcome: Amputation / Limb Salvage vs. Planned (Group 1)

At this time, there is not enough information regarding this endpoint. The data collection and planned analysis of this endpoint will be discussed in the next version of this SAP after the safety run-in and/or Simon Stage 1 analysis.

11.9 Disease Free Survival (Group 1)

Disease-free survival is defined as the time between the date of first dose of study drug and the date of recurrence/relapse or death from any cause, whichever occurs first.

At this time, there is not enough information regarding this endpoint. The data collection and planned analysis of this endpoint will be discussed in the next version of this SAP after the safety run-in and/or Simon Stage 1 analysis. However, Kaplan-Meier methods will be utilized for data analysis of this endpoint.

11.10 Local Recurrence-Free Survival, Time Frame: 2 Years (Group 1)

Local-recurrence-free survival is defined as time between the date of enrollment and the date of local recurrence/relapse or death from any cause, whichever occurs first.

At this time, there is not enough information regarding this endpoint. The data collection and planned analysis of this endpoint will be discussed in the next version of this SAP after the safety run-in and/or Simon Stage 1 analysis. However, Kaplan-Meier methods will be utilized for data analysis of this endpoint.

11.11 Distant Recurrence-Free Survival (Group 1)

Distant-recurrence free survival is defined as time between the date of enrollment and the date of distant recurrence/relapse or death from any cause, whichever occurs first.

At this time, there is not enough information regarding this endpoint. The data collection and planned analysis of this endpoint will be discussed in the next version of this SAP after the safety run-in and/or Simon Stage 1 analysis. However, Kaplan-Meier methods will be utilized for data analysis of this endpoint.

11.12 Symptomatic Disease Control (Group 1)

At this time, there is not enough information regarding this endpoint. The data collection and planned analysis of this endpoint will be discussed in the next version of this SAP after the safety run-in and/or Simon Stage 1 analysis.

11.13 Time to Local-Regional or Distant Progression (Group 3a)

Time to local-regional progression or distant progression is defined as the time between the date of enrollment and the date of local recurrence/relapse or distant progression.

At this time, there is not enough information regarding this endpoint. The data collection and planned analysis of this endpoint will be discussed in the next version of this SAP after the safety run-in and/or Simon Stage 1 analysis. However, Kaplan-Meier methods will be utilized for data analysis of this endpoint.

11.14 Local-Regional Control pre RECIST v1.1 (Group 3a)

At this time, there is not enough information regarding this endpoint. The data collection and planned analysis of this endpoint will be discussed in the next version of this SAP after the safety run-in and/or Simon Stage 1 analysis.

11.15 Exploratory Analysis: Target Lesions

Change in size of target lesion(s) including both injected, and non-injected tumors (if available) will be defined as the best percent change from baseline in the sum of diameters. This will be represented by a standard waterfall figure that is typically used to portray this efficacy parameter.

11.16 Exploratory Analysis: Target Lesions

DoR of target lesion(s) (including both injected, if available, and non-injected tumors) is defined as the time recorded between the date of enrollment and the date of the initial objectively documented tumor progression per RECIST v1.1, date of death from any cause, or the date of subsequent therapy, whichever occurs first. DoR will be evaluated for responders (i.e., participants with confirmed CR or PR) only.

11.17 Exploratory Analysis: Landmark Analysis

Landmark analyses (e.g., overall survival at 12, 24 months) will be conducted as deemed appropriate given the data and indication. If conducted, this exploratory analysis will be discussed in the clinical study report.

12. SAFETY ANALYSIS

Safety and tolerability will be summarized using AEs, SAEs, DLTs, deaths, events of special interest, events leading to dose reductions/modifications, discontinuation, and laboratory parameters.

All treatment-emergent AEs will be summarized by system organ class and preferred terms within a system organ class for each treatment group and Grade per NCI-CTCAE (version 5). Only treatment-emergent AEs will be summarized in the tables. Treatment-emergent AEs are those that occur after the first dose of Investigational Product is given. Each preferred term will be counted only once for a given patient. The severity (intensity) and the relationship to study medication will be summarized by system organ class and preferred term within a system organ class for each treatment group. For severity, if a patient has multiple occurrences of the same preferred term, the highest severity will be assumed.

Changes from baseline through the end of study will be descriptively summarized for the following: vital signs, ECG, ECHO/MUGA, coagulation, urinalysis, hematology, and clinical chemistry parameters. Tolerance and toxicity of SQ3370 treatment regimen will be assessed through evaluation of physical examinations, vital signs, laboratory parameters, AEs including DLTs, and all causes of mortality. The baseline definition for safety assessment is either at screening or prior to receiving the first dose of study drug; whichever is latest.

The Safety Analysis set defined as all patients who received at least 1 dose of SQL70 biopolymer and/or SQP33 protodrug will be utilized for all safety analyses.

In addition to the summary tables, safety data will also be presented in the individual patient listings.

12.1 Treatment Emergent Adverse Events

Treatment-emergent adverse events (TEAEs) are defined as all AEs that begin on or after the date of the first administration of study drug. Related AEs are those reported as possibly related to SQL70 biopolymer, related to SPQ33 protodrug, and related to SQ3370 (both SQL70 and SQP33). The verbatim terms of the TEAEs will be coded to preferred terms (PT) and system organ classes (SOC) per the Medical Dictionary for Regulatory Activities (MedDRA®) Version 24.1.

All reported AEs (including non-TEAEs) will be listed, documenting all information collected on the eCRF including verbatim term, MedDRA preferred term, MedDRA system organ class, start date, stop date, severity and relationship to SQ3370 treatment, relationship to SQL70 biopolymer, relationship to SQP33 protodrug, action taken, and outcome.

The TEAEs will be graded by the Investigator in terms of:

- Severity graded 1-5 according to CTCAE v5.0:
 - 1=Mild, 2=Moderate, 3=Severe, 4= Life Threatening, 5=Fatal.
- Relation to SQ3370:
 - 'Related' includes events where the causality was reported as related to SQL70 biopolymer, related to SPQ33 protodrug, related to SQ3370 treatment (both SQL70 and SQP33), or where the relationship was not reported on the eCRF.
 - 'Not Related' includes events where the study drug causality was reported 'Not Related' on the eCRF.

All TEAE summary tables will be presented with the number and percentages of patients in the Safety population. Incidence rates of treatment-emergent adverse events (TEAEs) will be summarized within each dose level at the Medical Dictionary for Regulatory Activities

(MedDRA) primary system organ class levels and preferred term. Patients may be counted under multiple system organ class (SOC) and preferred terms (PT), but for each SOC and PT category, patients are only counted once. If a patient has the same AE on multiple occasions, the highest severity grade (fatal > life threatening > severe > moderate > mild) or drug relationship (related > not related) recorded for the event will be summarized.

This list includes:

- All TEAEs
- All TEAEs graded severity
- All Related TEAEs to SQ3370 treatment
- All Related TEAEs to SQ3370 treatment graded by severity
- All Related TEAEs to SQL70 biopolymer
- All Related TEAEs to SQL70 biopolymer graded by severity
- All Related TEAEs to SQP33 protodrug
- All Related TEAEs to SQP33 protodrug graded by severity
- Serious TEAEs
- Adverse Event of Special Interest (AESI)
- Dose Limiting Toxicity (DLT)
- TEAEs leading to discontinuation from study
- TEAEs resulting in death.

Separate patient listings will be provided for all SAEs, AEs leading to study discontinuation, DLTs, AESIs, and deaths.

12.2 Serious Adverse Events

Incidence rates of serious TEAEs will be summarized within each dose level at the Medical Dictionary for Regulatory Activities (MedDRA) primary system organ class levels and preferred term A listing of patients who reported a serious adverse event will be presented. The data will be obtained from the AE dataset where 'Is this adverse event serious? is checked 'Yes'.

12.3 Adverse Events Leading to Discontinuation from Study

Incidence rates of TEAEs leading to discontinuation from study will be summarized within each dose level at the Medical Dictionary for Regulatory Activities (MedDRA) primary system organ class levels and preferred term. A listing of patients and the adverse events which led to study discontinuation from the study will be included. The specific AE will be identified from the AE dataset where 'Discontinued Study' is checked or has data within in.

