Patients will enroll at the RP2D of SQP33 given over 5 days and will receive a fixed dose of SQL70 (10 mL) on Day 1 of each cycle, except for patients with a secondary lymph node lesion. These patients may receive an additional 10 mL in that lesion for a total of 20 mL of SQL70 injection. All subjects will commence treatment with SQP33 within 3 hours ± 30 minutes.

Any patient at any point who has been determined to have progressive disease has reached the End of Treatment, any subject completing 12 cycles of treatment will have been deemed to have reached the end of treatment. See [Schedule of Assessments Appendix K](#).

Note: All patients in Phase 2a expansion groups who are no longer on treatment should begin Long Term Follow Up per the [Schedule of Assessments](#).

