3.1.5. End of Treatment

The patient, Investigators, and/or the Sponsor may decide to end a patient's treatment at any time. The Safety Follow-Up Visit should be performed approximately 30 days after the last dose of study drug (see section [3.1.6 Safety Follow-Up Visit](#)).

Reasons that the patient, Investigators, and/or the Sponsor may decide to end (discontinue) a patient's treatment include:

- Radiographic progression of disease per RECIST v1.1
- Unacceptable AE(s)
- Initiation of radiotherapy or non-protocol tumor directed treatment
- Any medical condition or treatment that the Investigator or Sponsor determines may jeopardize the patient's safety if he or she continues in the study
- Patient noncompliance with study procedures
- Patient inability to attend visits (e.g., patient moves, change in caregiver)

- Patient withdrawal of consent to treatment
- Patient withdrawal of consent to treatment and follow-up
- Investigator decision
- Sponsor decision
- Lost to follow-up
- Death

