3.1.7. Long Term Follow-Up

Long Term Follow-Up visits commence after the patient's last cycle of treatment, every 12 weeks (± 7 days) for up to two years. See [Schedule of Assessments](#) for the list of procedures performed at the visits.

All patients that discontinue treatment will be followed for information on progression, if treatment discontinuation was not RECIST 1.1 progression, and overall survival. Additional information will be obtained for next line of treatment and survival status.

[figure not shown]
This long term follow-up information will be gathered during routine clinic visits, other study site contact with the subjects, or via telephone or e-mail with the subjects/caregivers or referring physician offices.

If the study is closed, Long Term Follow-Up visits will stop.

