7.1.1.3. Action Taken for Adverse Events

The investigator or designee will record the action(s) taken with respect to study drug for the AE in the eCRF. Actions taken but not limited to:

- None/Dosed Not Changed: The study drug schedule was not changed.
- Drug Interrupted: The study drug schedule was modified by temporarily terminating the prescribed regimen of medication.
- Drug Withdrawn: the study drug schedule was modified through termination of the prescribed regimen of medication.
- Drug Reduced: The study drug schedule was modified by subtraction, either by changing the frequency, strength, or amount.
- Not Applicable: If the AE started after the End of Treatment date.

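### The Phase 2a SAP's only table of discontinuations by AE term counts exits from the study, so it omits patients who stop SQ3370 for toxicity but stay in follow-up

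*SAP*

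**What the plan says.** The list of TEAE tables in Phase 2a SAP 12.1 has one discontinuation entry: "TEAEs leading to discontinuation from study". Section 12.3 defines it: "Incidence rates of TEAEs leading to discontinuation from study will be summarized within each dose level". It also gives the selection rule: "The specific AE will be identified from the AE dataset where 'Discontinued Study' is checked or has data within in". The Phase 1 SAP has the same entry in its 12.1 list and the same 12.3.

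The protocol treats stopping treatment and leaving the study as different events.

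- Protocol 3.1.5 (End of Treatment) lists unacceptable AEs among the reasons to end treatment.
- Protocol 3.1.4.1 notes: "All patients in Phase 2a expansion groups who are no longer on treatment should begin Long Term Follow Up".
- Protocol 3.1.7 says: "All patients that discontinue treatment will be followed for information on progression, if treatment discontinuation was not RECIST 1.1 progression, and overall survival". Visits run every 12 weeks for up to two years.
- Protocol 6.21 ends a patient's study participation only when long-term follow-up is not entered or comes to an end.

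The action taken with study drug is recorded in the eCRF for each AE (Protocol 7.1.1.3). One category is "Drug Withdrawn: the study drug schedule was modified through termination of the prescribed regimen of medication". Interruption and reduction are separate categories. The opening of SAP section 12 commits to summarizing events that led to dose reductions or modifications and to discontinuation.

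**The concern.** A patient whose SQ3370 is stopped for toxicity, and who then follows the protocol, has not discontinued the study. Programmed literally, 12.3 leaves that patient out. Its count reflects the joint event of stopping for an AE and also leaving the study, which is not what a reader of a discontinuation table expects.

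Safety and tolerability is the primary objective of both phases. In Group 2 it includes comparing the 3-day and 5-day schedules, with 11 patients per arm. At that size, two or three toxicity-driven stops are a visible signal, and the terms and grades behind them are what would separate the schedules. No table in 12.1 to 12.6 links AE terms to a treatment stop, reduction or interruption.

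**Working it through.** **Step 1: is 'study' only loose wording for 'treatment'?** The SAP's own usage says not. SAP 10.2 lists reasons for treatment discontinuation and reasons for study discontinuation as separate items. SAP 2.3 describes Group 1 patients who come off treatment for post-operative radiation and remain on study in long-term follow-up. The toxicity rules in the protocol also act on treatment: myocardial injury (7.1.2.2, 7.5.4), Grade 3-4 infusion reactions (7.5.2) and suspected drug-induced liver injury (7.5.6) stop study treatment. None of them removes the patient from the study.

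**Step 2: who reaches the 12.3 table?** Taking the protocol rules together, a patient who stops for an AE reaches it only by also leaving the study, for example by withdrawing consent to follow-up, being lost to follow-up or dying.

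**Step 3: size.** The plan states no figure to reproduce, so this is an illustration.

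- N = 46 + 22 + 26 = 94 planned Phase 2a patients (Protocol 3.3; Table 4).
- s = share stopping SQ3370 for an AE (assumed).
- f = share of those who also leave the study (assumed).
- A treatment-based table shows N × s, rounded to whole patients. The 12.3 table shows on average N × s × f.

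| s | Treatment-based table | 12.3 table, f = 0 | f = 10% | f = 25% | f = 50% |
|---|---|---|---|---|---|
| 5% | 5 (5.3%) | 0 | 0.5 (0.5%) | 1.25 (1.3%) | 2.5 (2.7%) |
| 10% | 9 (9.6%) | 0 | 0.9 (1.0%) | 2.25 (2.4%) | 4.5 (4.8%) |
| 20% | 19 (20.2%) | 0 | 1.9 (2.0%) | 4.75 (5.1%) | 9.5 (10.1%) |

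For example, at s = 10% and f = 50%: 9 × 0.5 = 4.5, and 4.5/94 = 4.8%, against 9/94 = 9.6%. On average the table misses a fraction 1 − f of the stops, so it misses more than half only when f is below 50%.

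In one Group 2 arm, if 3 of 11 patients stop for an AE (27%), the table shows 0/11 if all three enter follow-up and 1/11 (9%) if one of them leaves.

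**Step 4: what else is planned?**

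- SAP 10.2 counts reasons for treatment discontinuation by expansion group, and SAP 8.5 gives the 3-day and 5-day arms separate columns.
- SAP 10.8 summarizes interruptions and dose changes, without linking them to AEs.
- The AE listing in SAP 12.1 shows action taken for each event.

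None of these gives incidence by system organ class and preferred term, per arm, of the TEAEs that led to a change or stop of treatment.

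**The case against.** The strongest reply is that most of the information is reported somewhere. If 3 of 11 patients in an arm stop for an AE, the disposition table should show 3/11 in that arm's column, so the crude comparison of stop rates between schedules survives. Events such as cardiotoxicity and cytopenias also appear in the AESI table, the severity tables and the hematology shift tables. This stands, and it narrows the gap to the term-level tables.

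A reader might go further and infer that 12.3 is the main tolerability table and will be near zero in every arm whatever the true rate. The documents do not support either inference. The Phase 2a primary endpoint is the frequency of AEs and SAEs plus changes in safety measurements. The stated Group 2 toxicity rule uses Grade 3 or higher related anemia and febrile neutropenia against 15%, not discontinuations. How empty 12.3 would be depends on how sites complete 'Discontinued Study' and on how many patients also leave the study. The annotated CRF is not among the documents supplied, and the second quantity is not documented.

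It can also be said that the table shells, which SAP 8.4 describes as part of the SAP, were not available, and that Protocol 8.4.1 speaks of events leading to discontinuation without saying from what. The defect may therefore be a labelling slip in 12.1 and 12.3 rather than a decision to omit the analysis. That is possible, but the text names a specific selection field, and it is the text that will be programmed.

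**Conclusion.** The point holds as a gap in the specified safety tables. The only discontinuation table by AE term is keyed on leaving the study, so it omits AE-driven treatment stops in patients who follow the protocol into long-term follow-up. The AE-linked summaries promised in SAP section 12 have no listed table that delivers them for treatment.

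The size is not documented. With 10% of 94 patients stopping for an AE and 0 to 50% of those also leaving the study, the table would show about 0 to 4.8% instead of about 9.6%. Both shares are assumptions, and the result also assumes that 'Discontinued Study' is completed literally. The stops are not lost from the report as a whole; what is lost is which events caused them, tabulated by arm.

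**What to change.** In the Phase 2a SAP, which is still a draft (version 0.1 with a placeholder date):

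1. Add to the 12.1 list and to 12.3 a table of TEAEs leading to discontinuation of study treatment, by system organ class and preferred term and by the SAP 8.5 columns, selected where action taken is 'Drug Withdrawn'. Split it by SQL70 and SQP33 if action is recorded per component.
2. Add matching tables for 'Drug Reduced' and 'Drug Interrupted', which would deliver what SAP section 12 promises.
3. Keep the study-discontinuation output as a separate, clearly labelled item.
4. Check the annotated CRF to confirm what the 'Discontinued Study' field records.

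The Phase 1 SAP has the same wording but is already signed. There, add the tables by amendment or as a documented addition in the study report.

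The cost is a wording change and two or three extra tables from data already collected. No dose or clinical rule changes. Doing it now is simpler than later, because SAP 8.4 requires a SAP revision for additional unplanned analyses.

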12.4 Deaths Due to Adverse Event

Incidence rates of TEAEs leading to death will be summarized within each dose level at the MedDRA primary system organ class levels and preferred term. A listing of patients who died on study will be included. The specific AE leading to death will be identified from the AE dataset where 'Did the adverse event result in death? is checked 'Yes'. Other possibilities are Outcome=Fatal and/or CTCAE Grade=5.

12.5 Adverse Event of Special Interest (AESI)

Incidence rates of TEAEs of special interest will be summarized within each dose level at the MedDRA primary system organ class levels and preferred term. All AESIs will be listed by expansion group and patient.

AESIs will be defined as the preferred terms of potential myocardial toxicity, COVID-19 infections, and AEs due to overdose. The specific AESI will be identified from the AE dataset where AESI is checked.

12.6 Dose Limiting Toxicity (DLT)

Dose limiting toxicities are not part of the dose expansion part of this protocol. The Phase 1 dose escalation SAP contains details on DLTs. There should be no DLTs identified for Phase 2a dose expansion.

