7.1.2. Definition of Adverse Events of Special Interest (AESI)

An AESI is one of scientific and medical concern specific to the study drug, which requires ongoing safety monitoring and prompt communication by the investigator to the sponsor. Depending on the nature of the event, Regulatory Authorities should be notified. Per ICH E2F such an event might require further investigation in order to characterize and understand it.

AESIs in this study include Dose-limiting Toxicities (DLTs), potential myocardial toxicity, COVID-19 infections, and AEs due to overdose.

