8.4. STATISTICAL ANALYSES

8.4.1. Safety Analyses

Safety and tolerability will be summarized using AEs, SAEs, DLTs, deaths, events of special interest, events leading to discontinuation, and laboratory parameters for all participants who have received at least 1 dose of study treatment. All treatment-emergent AEs will be summarized by system organ class and preferred terms within a system organ class for each treatment group and Grade per NCI-CTCAE (version 5). Only treatment-emergent AEs will be summarized in the tables. Treatment-emergent AEs are those that occur after the first dose of Investigational Product is given. Each preferred term will be counted only once for a given patient. The severity (intensity) and the relationship to study medication will be summarized by system organ class and preferred term within a system organ class for each treatment group. For severity, if a patient has multiple occurrences of the same preferred term, the highest severity will be assumed. Changes from baseline through the end of study will be descriptively summarized for the following: vital signs, ECG, ECHO/MUGA, coagulation, urinalysis, hematology, and clinical chemistry parameters.

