3.4 Safety Endpoints

Frequency of adverse events (AEs), Serious Adverse Events (SAEs) and dose-limiting toxicities (DLTs), as well as changes from baseline in vital signs, clinical laboratory parameters, physical examination findings, ECHO/MUGA, and electrocardiogram (ECG) results.

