10.8 Study Drug Administration: Exposure and Modifications

The SQ3370 Investigational Product consists of 2 components:

- (1) Intratumoral injection of a prodrug activating biopolymer (SQL70: 10 mL or 20 mL).

(2) Five (or three) consecutive days of intravenous (IV) infusions of a trans-cyclooctene (TCO)-modified protodrug of Dox with attenuated cytotoxic activity (SQP33) for a 21-day cycle.

An individual cycle of treatment is defined as a 3-week (21-day) period wherein the SQL70 biopolymer is injected into a lesion or lesions on Day 1 followed by 3-5 consecutive daily infusions of SQP33 protodrug (Day 1-5 or in Phase 2a Group 2 subset will receive Day 1-3). In Phase 1 patients assigned to receive 20 mL SQL70, no more than 2 lesions may be injected (10 mL each) during the treatment cycle with the exception of a “regional cluster of lesions” defined as tumors that are contiguous, in apposition to each other, or are within 5 cm of each other.

For Phase 2a the treatment regimens are:

- Group 1 Extremity STS: 20mL SQL70 Biopolymer + 250 mg/m² (12x Dox Eq)
SQP33 Protodrug on a 5 day infusion schedule
- Group 2 Unresectable STS :10mL SQL70 Biopolymer + 250 mg.m² (12x Dox Eq)
SQP33 Protodrug on a 5 day infusion schedule
- Group 2 Unresectable STS :10mL SQL70 Biopolymer + 250 mg.m² (12x Dox Eq)
SQP33 Protodrug on a 3 day infusion schedule
- Groups 3A Head and Neck:10mL SQL70 Biopolymer + 250 mg.m² (12x Dox Eq)
SQP33 Protodrug on a 5 day infusion schedule.

Study treatment (SQP33 and SQL70) received will be summarized as described below:

Study Drug Administration (Exposure):

- Number of cycles
- Duration of Therapy
- Average Duration of SQP33 Infusions
- Total SQP33 Cumulative Dose (mg/m²)
- Total SQL70 Cumulative Dose (mg/m²)
- Total Doxorubicin Equivalent Cumulative Dose (mg/m²)
- Highest SQP33 dose administered
- Highest Doxorubicin Equivalent dose administered

Dose Modifications:

1. SQL70 Biopolymer

- a. Injection interruption

- b. Dose increase of biopolymer (10 mL to 20 mL)
- 2. SQP33
 - a. Dose interruption of infusion (bag change is not an interruption)
 - b. Dose reduction (Y or N, and by summary units)
 - c. Dose increase (Y or N, and by summary units)

Details concerning the derivation of these measures are below.

- Highest SQP33 Dose Administered = Defined as the largest (or maximum) SQP33 dose administered (mg/m²)
- Total SQP33 Cumulative Dose received (mg/m²) = Defined as the sum of all SQP33 doses (mg/m²) received

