16. STATISTICAL ANALYSIS CHANGES FROM THE PROTOCOL

The analyses described are based on the final clinical study protocol SQ3370-101 Amendment 8 dated November 17, 2022. This SAP supersedes the statistical considerations identified in the protocol. The following table summarizes changes in the SAP versus the protocol:

| SAP | Protocol | Reason |
|-----|----------|--------|
| N/A | N/A | N/A |

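### Phase 2a SAP 12.6 rules out DLTs that the same SAP and the protocol say will be reported, including in the Group 1 run-in of 20 mL SQL70 with 12x SQP33

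*SAP*

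**What the plan says.** The Phase 2a SAP, Section 12.6, sends the reader to the Phase 1 SAP for DLTs and adds: "There should be no DLTs identified for Phase 2a dose expansion". Section 12.5 then defines the events of special interest (AESIs) without them: "AESIs will be defined as the preferred terms of potential myocardial toxicity, COVID-19 infections, and AEs due to overdose".

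Other parts of the plan say the opposite. SAP 3.4 gives the Phase 2a safety endpoint as "Frequency of adverse events (AEs), Serious Adverse Events (SAEs) and dose-limiting toxicities (DLTs". The opening of SAP 12 lists DLTs among the safety summaries. SAP 12.1 lists a DLT table and adds: "Separate patient listings will be provided for all SAEs, AEs leading to study discontinuation, DLTs, AESIs, and deaths". Protocol 7.1.2, with no limit to Phase 1, states: "AESIs in this study include Dose-limiting Toxicities (DLTs), potential myocardial toxicity, COVID-19 infections, and AEs due to overdose". Protocol 8.4.1 states: "Safety and tolerability will be summarized using AEs, SAEs, DLTs, deaths, events of special interest, events leading to discontinuation".

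SAP 16 declares: "This SAP supersedes the statistical considerations identified in the protocol". Its table of changes from the protocol is filled with N/A.

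On conduct, Protocol 3.2.7 and SAP 7.1 have the SRC apply the same criteria in Phase 2a. In Protocol 3.2.7 these refer back to the DLT definition together with the members' clinical judgement. Group 1 has a run-in of six patients reviewed after Cycle 1. SAP 10.8 gives its regimen: "Group 1 Extremity STS: 20mL SQL70 Biopolymer + 250 mg/m² (12x Dox Eq".

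**The concern.** Safety is the primary objective of Phase 2a. The SAP names DLT frequency as a safety endpoint, promises a table and a listing for it, and then says there should be nothing to put in them. A programmer cannot follow both instructions. Because the SAP claims precedence over the protocol's statistical text and records no change, the report could show no DLTs in Phase 2a because none were looked for.

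The Group 1 run-in is where this is most likely to matter. Protocol 3.2.7 justifies that run-in by the 20 mL volume, and the SRC's decision there draws on the DLT definition. The decision would use a classification that the analysis plan says should not be made.

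**Working it through.** **1. The Group 1 dose.** Inputs: 250 mg/m² SQP33, read as a daily dose, for 5 days (SAP 10.8); 0.7153 g doxorubicin HCl per g SQP33 (SAP 8.6); 75 mg/m² standard dose (Protocol 1.3.1).

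250 × 5 × 0.7153 / 75 = 894.1 / 75 = 11.92, which agrees with the stated 12x.

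Phase 1 experience with 20 mL from Cycle 1 (Protocol 1.4): five patients at 4x and three at 6x, eight in all. 12x / 6x = 2.

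**2. The texts side by side.**

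| Place | DLTs in Phase 2a |
|---|---|
| SAP 3.4 | Safety endpoint |
| SAP 12, opening | Part of the safety summary |
| SAP 12.1 | Table and separate listing |
| SAP 12.5 | Left out of the AESIs |
| SAP 12.6 | Not part of expansion; none should be identified |
| SAP 16 | No change from the protocol declared |
| Protocol 2.2.2.1 | Not named in the primary endpoint |
| Protocol 3.2.7 and SAP 7.1 | SRC uses the Phase 1 criteria |
| Protocol 7.1.2 | AESI, no phase limit |
| Protocol 8.4.1 | Part of the safety summary |

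Only SAP 12.5, SAP 12.6 and Protocol 2.2.2.1 point towards leaving DLTs out.

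**3. One event traced through.** Suppose a run-in patient has related febrile neutropenia in Cycle 1. It meets Protocol 3.2.6. Under Protocol 7.1.2 and 7.2 it is an AESI to be reported within 24 hours. Under SAP 12.1 it appears in the graded and related adverse-event tables. Under SAP 12.6 it is not identified as a DLT, so the DLT table and listing promised in 12.1 omit it.

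**4. How often this could arise.** Table 10 of Protocol 8.3 gives a historical febrile neutropenia rate of about 20%, without a time window, so the Cycle 1 rate may be lower. The rates below are assumptions. With n = 6, P(at least one) = 1 − (1 − p)⁶, and P(at least two) is the exact binomial tail.

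| Assumed rate per patient in Cycle 1 | P(≥1 of 6) | P(≥2 of 6) |
|---|---|---|
| 5% | 26.5% | 3.3% |
| 10% | 46.9% | 11.4% |
| 15% | 62.3% | 22.4% |
| 20% | 73.8% | 34.5% |

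The first probability is the chance that the run-in yields an event which 12.6 would leave unlabelled. The second bears only on the clarification under fix. Other toxicities in 3.2.6 would raise both.

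**5. Blood counts in Group 1, Cycle 1** (Protocol Appendix H). Haematology is scheduled on Days 1 to 5 and Day 10 ± 2, then on Day 1 of the next cycle (study day 22), drawable up to 3 days early. Going by those windows, the gap without a scheduled count runs from 7 days (Day 12 to Day 19) to 14 days (Day 8 to Day 22), and longer if the Day 10 sample is itself drawn early. Phase 1 had a count at Day 17 (Appendix G); Group 1 does not.

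**The case against.** The best defence is that 12.6 is deliberate. Protocol 3.2.6 sits under Phase 1 dose escalation, Protocol 2.2.2.1 leaves DLTs out of the Phase 2a primary endpoint, and the lighter blood-count schedule fits that choice. On this view the DLT entries in SAP 3.4, 12 and 12.1 are carry-over from the Phase 1 SAP, and the version 0.1 footer suggests harmonisation is pending. This is a fair reading of some of the text. It does not explain Protocol 7.1.2 and 8.4.1 or the N/A change table, and it leaves the SRC's criteria without their main term.

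A reader might infer that run-in patients go unprotected. The documents do not support that. The SRC sees all available safety data and uses judgement, safety is assessed continuously (Protocol 8.3), a second look is set at N=15, and the SAP cannot switch off 24-hour reporting under the protocol. SAP 12.5 also finds AESIs by a checked box, so a DLT reported as an AESI would still be listed.

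A reader might also infer that the run-in has no stopping limit. No count is written for Group 1, but applying the same criteria can be read as carrying over the Phase 1 limit of two patients (Protocol 3.2.2). That is missing detail, not an error.

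A third inference is that anaemia must be added to the DLT list, because Group 2 has a 15% limit that includes it and because Phase 1 reported Grade ≥3 anaemia in 3/8 with 20 mL (37.5%, exact 95% CI 8.5% to 75.5%) against 4 with 10 mL (16.7%, implied n = 24, CI 4.7% to 37.4%). The Fisher p-value is 0.33. Cycle and relatedness are not given. Phase 1 patients were refractory, relapsed or ineligible for standard care, and could have had up to 300 mg/m² prior doxorubicin, whereas Group 1 has had no chemotherapy for STS. Transfusion is permitted in Phase 2a, and entry haemoglobin may be 9.0 g/dL, about 1 g/dL above the Grade 3 cut-off. The 15% limit would not transfer neatly either, since 1/6 is already 16.7%. Counting anaemia is a trade-off on which the documents do not settle the answer.

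**Conclusion.** The point stands as an internal contradiction with a reporting consequence. SAP 12.6 and 12.5 disagree with three sections of the same SAP and two of the protocol, and with the basis on which the SRC reviews a combination at twice the Phase 1 SQP33 dose for that volume. What would be lost is the correct classification of an event in a listed safety endpoint. Sight of the event would not be lost.

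The chance that the run-in produces such an event is about 27% to 74% for febrile neutropenia alone, if the Cycle 1 rate per patient lies between 5% and 20%. The upper figure borrows the historical doxorubicin rate in Table 10, and the lower end is an assumption. The contradiction itself rests on the text and does not depend on these rates.

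**What to change.** 1. In SAP 12.6, replace the statement that none should be identified with: *Cycle 1 toxicities meeting Protocol 3.2.6 in Phase 2a run-in patients will be flagged and tabulated by expansion group.*
2. In SAP 12.5, restore DLTs to the AESI list, as in Protocol 7.1.2.
3. As a clarification only, SAP 7.1 may state that the same criteria include the existing limit of two patients with a 3.2.6 DLT, applied to the six-patient Group 1 run-in.

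Items 1 and 2 change one sentence and one term. They need a DLT flag in the Phase 2a adverse-event data. The Phase 1 SAP uses one (AEDLT, Section 12.6), but the Phase 2a SAP names none. Grade 4 neutropenia or thrombocytopenia is a DLT only if it lasts more than 7 days, so deciding such a case may take an unscheduled count between Day 10 and the next cycle. Item 3, read as binding, would be reached in 3.3% to 34.5% of run-ins at febrile neutropenia rates of 5% to 20%.
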